7.14 Dosing plan

Cohorts of 3 patients will be treated at a dose level at a time (see Section 16.0). The study will temporarily close between patient cohorts. Doses will not be escalated in any individual patient.

7.15 Duration of treatment

Duration of treatment is a maximum of 12 months from start of Cycle 1. If a patient remains on cycles with a length of 21 days without treatment delays, this will be 18 cycles total. If the cycle length is increased due to dosing frequency changes or dose delays, the number of cycles will be reduced to not exceed 12 months of treatment total. If a patient is continuing to benefit from treatment after 12 months, he or she may continue to receive pembrolizumab every 3 weeks for up to 24 months total from start of cycle 1 at the investigator/sponsor discretion. If a patient achieved CR before Cycle 5, the patient will continue through Cycle 6 and could stop at the discretion of the treating provider and investigator. If a patient achieved CR at or after Cycle 5, the patient could continue treatment for 2 more cycles at the discretion of treating provider.

#### 7.16 Dose Limiting Criteria (DLT)

For this protocol, DLT will be defined as an adverse event attributed (definitely, probably, or possibly) to the study treatment during the first two cycles of treatment AND meeting the following criteria.

CTCAE System Organ Class	DLT Definition (CTCAE v4)
Investigations Neutrophil count decreased Platelet count decreased	≥Grade 4 ANC or PLT for ≥7 days
Infections and infestations Other, specify	Any ≥ Grade 3
Blood and lymphatic system disorders Febrile neutropenia	Defined as fever ≥38.5°C (38 >1 hour) with grade ≥4 neutropenia
Skin and subcutaneous tissue disorders Erythema multiforme Skin ulceration Urticaria	≥ Grade 3 erythema multiforme, ulceration, or urticaria that does not resolve to <Grade 2 within three weeks
Respiratory, thoracic and mediastinal disorders Bronchial obstruction Pneumonitis Wheezing	≥Grade 3 bronchial obstruction, pneumonitis, or wheezing
Immune system disorders Allergic reaction Autoimmune disorder	≥Grade 3 allergic reaction or autoimmunity
All Other Non-Hematologic	≥Grade 3 that does not resolve to < Grade 2 ≤ 72 hours per NCI Common Terminology Criteria for Adverse Events

Note: any adverse event that leads to a permanent discontinuation of the study agent is considered a DLT.

#### 7.17 Dose levels

The dose level of pembrolizumab is fixed at 200 mg IV on Day 1 of every 21 days. The DLT criteria will be used to determine the timing of the subsequent administration of pembrolizumab, not for adjustment of the dose level. The dose interval may be increased by 7 days each time, the maximum dosing interval allowed is 8 weeks.

The study involves DC injection at only one dose level, but has potentially multiple injections over time. The DLT criteria will be used to determine timing of the subsequent administration of DC, and not for adjustment of DC dose level.

**Note: This study will not allow dose reduction, only dose interval changes.**

## **7.2 Patients experiencing a DLT**

Investigators are to contact the Study Chair as soon as any DLT occurs. Patients who experience DLT will go to observation.

## **7.3 Continued pembrolizumab treatment**

Patients may continue on pembrolizumab treatment for 1 year after initial treatment is terminated (please check with Study Chair).

## **7.4 Retreatment**

Patients who qualify for retreatment (see Section 13.0) will not change dose levels and will follow the original treatment schedule starting at cycle 2. When retreating, new baseline disease measurement will be established. The new baseline disease measurement will be the disease measurement at the end of the cycle prior to the retreatment. Patients may receive all DC according to schedule as long as they do not have continued progression of disease, develop major adverse events, and have DC available.

Patients will not undergo any additional leukapheresis for the purpose of manufacturing additional DC.

## **7.5 Phase II**

Treatment schedule for phase II will be defined as the treatment regimen from the MTD dose schedule in phase I.

NOTE: Phase II's dose schedule will follow Phase I Dose Level I (See Section 7.1)

## **8.0 Dosage Modification Based on Adverse Events**

### **8.1 Treatment schedule modifications in patients based on adverse events**

8.11 Patients will be evaluated by the study team prior to each dose of DC for an adverse event check. Determination will be made if the adverse event is treatment related (possible, probable or definite), i.e. a toxicity (see Section 10; Adverse event monitoring and reporting). If any adverse event has occurred, then the treatment schedule will be modified as in 8.12, 8.13, or 8.2. For cycles involving only pembrolizumab treatments (Cycles 1 and 6-18 for dose level 1 and Cycles 1 and 8-18 for dose level -1), refer to Section 8.2.

8.12 For Grade 1/2 adverse event during cycles with DC injections (Cycles 2 – 5 for dose level 1 and Cycles 2 – 7 for dose level -1): We will allow a delay in DC treatment up to four weeks for dermatological AEs  $\leq$  Grade 2; for all other Grade 1/2 adverse events not listed in Table 7.16 or 8.2, no change in procedure is required or expected.

8.13 For Grade 2/3/4 adverse events (Grade 2/3/4 described in Table 8.2 or

any grade 3/4), pembrolizumab dose schedule will be modified as described in Table 8.2. DC and Pevnar13 injections for the cycle in which pembrolizumab are delayed will also be delayed and resumed when pembrolizumab resumption criteria has been met. For a grade 2/3/4 adverse event per Table 7.16 that is attributed to treatment and does not resolve within two weeks, if the patient has not completed all treatments, he or she will not receive any further treatment on this trial. The patient will go to observation phase.

## 8.2 Treatment schedule modifications for pembrolizumab

Adverse events (both non-serious and serious) associated with pembrolizumab exposure may represent an immunologic etiology. These adverse events may occur shortly after the first dose or several months after the last dose of treatment. Pembrolizumab must be withheld for drug-related toxicities and severe or life-threatening AEs per Table 8.21 below. See Section 9.0 for supportive care guidelines, including use of corticosteroids.

**Table 8.21** Dose Modification Guidelines for Drug-Related Adverse Events for Pembrolizumab

CTCAE System/Organ/Class (SOC)	Adverse Event	Hold Treatment for Grade	Timing for Restarting Treatment	Treatment Discontinuation
Gastrointestinal disorders	Diarrhea or Colitis	2-3	AE resolves to Grade 0-1	AE does not resolve within 12 weeks of last dose or inability to reduce corticosteroid to 10 mg or less of prednisone or equivalent per day within 12 weeks
		4	Permanently discontinue	Permanently discontinue
Investigations	AST, or ALT, or Blood bilirubin	2	AE resolves to Grade 0-1	AE does not resolve within 12 weeks of last dose.
		3-4	Permanently discontinue (see exception below) a	Permanently discontinue
Metabolism and nutrition disorders	Glucose intolerance (Type 1 diabetes mellitus [if new onset]) or Hyperglycemia	T1DM or 3-4	Hold pembrolizumab for new onset Type 1 diabetes mellitus or Grade 3-4 hyperglycemia associated with evidence of beta cell failure	Resume pembrolizumab when patients are clinically and metabolically stable.
Endocrine disorders	Endocrine disorders – Other, specify: Hypophysitis	2-4	AE resolves to Grade 0-1. Therapy with pembrolizumab can be continued while endocrine replacement therapy is instituted	AE does not resolve within 12 weeks of last dose or inability to reduce corticosteroid to 10 mg or less of prednisone or equivalent per day within 12 weeks

CTCAE System/Organ/Class (SOC)	Adverse Event	Hold Treatment for Grade	Timing for Restarting Treatment	Treatment Discontinuation
Endocrine disorders	Hyperthyroidism	3	AE resolves to Grade 0-1	AE does not resolve within 12 weeks of last dose or inability to reduce corticosteroid to 10 mg or less of prednisone or equivalent per day within 12 weeks
		4	Permanently discontinue	Permanently discontinue
Endocrine disorders	Hypothyroidism	2	Therapy with pembrolizumab can be continued while thyroid replacement therapy is instituted	Therapy with pembrolizumab can be continued while thyroid replacement therapy is instituted
General disorders and administration site conditions	Infusion related reaction	2 b	AE resolves to Grade 0-1	Permanently discontinue if AE develops despite adequate premedication
		3-4	Permanently discontinue	Permanently discontinue
Respiratory, thoracic and mediastinal disorders	Pneumonitis	2	AE resolves to Grade 0-1	AE does not resolve within 12 weeks of last dose or inability to reduce corticosteroid to 10 mg or less of prednisone or equivalent per day within 12 weeks
		3-4	Permanently discontinue	Permanently discontinue
Renal and urinary disorders	Acute kidney injury or Chronic kidney disease (e.g. Renal failure or Nephritis)	2	AE resolves to Grade 0-1	AE does not resolve within 12 weeks of last dose or inability to reduce corticosteroid to 10 mg or less of prednisone or equivalent per day within 12 weeks
		3-4	Permanently discontinue	Permanently discontinue
	All Other Drug-Related Adverse Events c	3	AE resolves to Grade 0-1	AE does not resolve within 12 weeks of last dose or inability to reduce corticosteroid to 10 mg or less of prednisone or equivalent per day within 12 weeks
		4	Permanently discontinue	Permanently discontinue

CTCAE System/Organ/Class (SOC)	Adverse Event	Hold Treatment for Grade	Timing for Restarting Treatment	Treatment Discontinuation
Note: Permanently discontinue for any severe or Grade 3 drug-related AE that recurs or any life-threatening event.				
a For patients with liver metastasis who begin treatment with Grade 2 AST or ALT, if AST or ALT increases by greater than or equal to 50% relative to baseline and lasts for at least 1 week then patients should be discontinued.				
b If symptoms resolve within one hour of stopping drug infusion, the infusion may be restarted at 50% of the original infusion rate (e.g., from 100 mL/hr to 50 mL/hr). Otherwise dosing will be held until symptoms resolve and the subject should be premedicated for the next scheduled dose.				
c Patients with intolerable or persistent Grade 2 drug-related AE may hold study medication at physician discretion. Permanently discontinue study drug for persistent Grade 2 adverse reactions for which treatment with study drug has been held, that do not recover to Grade 0-1 within 12 weeks of the last dose.				

Note: The term “interruption” has the same meaning as “delay”.

8.21 Other instructions for pembrolizumab

If pembrolizumab-related toxicity does not resolve to Grade 0-1 within 12 weeks after last administration of study drug, study therapy discontinuation is recommended. With Investigator agreement, patients with a laboratory adverse event still at Grade 2 may continue in the study only if asymptomatic and controlled.

In patients who continue on study therapy after experiencing an Adverse Event warranting potential dose modification, if considered drug-related by the investigator, once the patient has recovered to Grade 0-1 the dosing interval in subsequent cycles will be increased by 1 week (e.g., to 3 weeks in patients who were on an every 2-week schedule). Following each such dose delay due to toxicity, the dosing interval should increase by an additional week. For example, patients who began the study on a 3-week dosing schedule, and have stopped drug twice for due to a drug-related toxicity that meets the above criteria, should now be dosing every 5 weeks.

For patients who experience a recurrence of the same severe AEs listed above with rechallenge of pembrolizumab, a consultation with the Investigator will occur to determine whether the patient should continue in the study. A patient who experiences the same SAE of the same NCI CTCAE grade or higher with rechallenge of pembrolizumab must discontinue pembrolizumab immediately.

Reduced dose of pembrolizumab dose (ie, below 200 mg) will not be administered.

Dosing interruptions are permitted in the case of medical / surgical events or logistical reasons not related to study therapy (e.g., elective surgery, unrelated medical events, patient vacation, and/or holidays). Subjects should be placed back on study therapy within 3 weeks of the scheduled interruption, unless otherwise discussed with the Study Chair. The reason for interruption should be documented in the patient's study record.

**Pembrolizumab (MK-3475) will be withheld for drug-related Grade 4 hematologic toxicities per table in 8.3, non-hematological toxicity  $\geq$  Grade 3 including uncontrolled laboratory abnormalities, and severe or life-threatening AEs per Tables in 8.2 and 8.3.**

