### 8.3 Dose Modification for Hematological Toxicities (Platelet and Hemoglobin only) for all agents

Note: hematological toxicity is not based on CTCAE 4.0 except neutrophil, but based on lymphoma specific hematological toxicity.

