#### Dose modification guidelines for drug-related hematological (hemoglobin and platelets) adverse events

Toxicity	Grade 	Decrease from pretreatment	Hold Treatment (Y/N)	Timing for restarting treatment	Dose/Schedule for restarting treatment	Discontinue Subject (after consultation with PI)
NHL specific Hematological Toxicity	1	11-24% decrease in HGB or PLT	No	N/A	N/A	N/A
	2	25-49% decrease in HGB or PLT				
	3	50-74% decrease in HGB or PLT	Yes	Toxicity resolves to Grade 0-2 or baseline	May increase the dosing interval by 1 week	Toxicity does not resolve within 8 weeks of last infusion
	4	$\geq$ 75% decrease in HGB or PLT	Yes	Toxicity resolves to Grade 0-2 or baseline	May increase the dosing interval by 1 week	Permanent discontinuation should be considered for any severe or life-threatening event. Go to observation if $\geq$ 2 cycles of therapy were given, otherwise go to event monitoring

 If, at any level of decrease from the baseline value the platelet and/or hemoglobin counts are within normal limits or platelet count is still  $\geq$  100,000/ $\mu$ L, this will be considered a grade 0.

 If patient has persistent cytopenia, it is recommended to repeat bone marrow evaluation to test if there is disease progression.

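### Section 8.21 names only Grade 4 hematologic toxicity as a reason to hold pembrolizumab, but the 8.3 table it cites also holds at Grade 3

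*Combined protocol and SAP*

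**What the plan says.** Section 8.21 ends with a bold instruction listing three grounds for withholding pembrolizumab. The first is that it "will be withheld for drug-related Grade 4 hematologic toxicities per table in 8.3". The second is non-hematological toxicity of Grade 3 or higher. The third is "severe or life-threatening AEs per Tables in 8.2 and 8.3", with no grade attached.

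Section 8.3 is headed "Dose Modification for Hematological Toxicities (Platelet and Hemoglobin only) for all agents", so it governs pembrolizumab along with the other agents. It uses its own scale: "hematological toxicity is not based on CTCAE 4.0 except neutrophil, but based on lymphoma specific hematological toxicity". In its table, Grade 3 is "50-74% decrease in HGB or PLT" with hold marked Yes. Grade 4 (at least a "75% decrease in HGB or PLT") is also marked Yes, and permanent discontinuation is to be considered. Footnote 1 resets to Grade 0 any value within normal limits and any platelet count still at or above 100,000/µL.

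Two other provisions bear on Grade 3. Section 8.13 covers cycles with dendritic cell injections and says that for "any grade 3/4), pembrolizumab dose schedule will be modified as described in Table 8.2". Table 8.21 has a row for "All Other Drug-Related Adverse Events" that holds at Grade 3.

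**The concern.** The sentence points to a table as its authority and then gives a different threshold from that table. Placing Grade 4 for hematologic toxicity next to Grade 3 or higher for non-hematological toxicity makes the difference look intended. A reader could conclude that a Grade 3 fall in hemoglobin or platelets need not be held.

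The position of the sentence adds to this. Section 8.11 sends staff to Section 8.2 for the pembrolizumab-only cycles. On the phase II schedule these are Cycle 1 and Cycles 6 to 18, which is 1 + 13 = 14 of 18 cycles. The bold sentence is the closing instruction of that section and its pointer to 8.3. At stake is dosing a patient whom the table says to hold. Sections 15.17 and 15.202 list immune thrombocytopenia and hemolytic anemia among the reported risks of pembrolizumab, so such falls are not purely hypothetical.

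**Working it through.** The plan states no figure to reproduce. The check compares the two rules and then works out where they give different answers.

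**The two rules for a drug-related fall in hemoglobin or platelets**

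| Grade on the 8.3 scale | Fall from pretreatment | 8.3 table | Hematologic clause of the bold sentence in 8.21 |
|---|---|---|---|
| 3 | 50–74% | Hold | Not named |
| 4 | 75% or more | Hold | Hold |

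The rules part company for a Grade 3 fall that footnote 1 does not reset to Grade 0.

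**Inputs.** The minimum baselines come from Section 3.17: platelets 50,000/mm³ and hemoglobin 8.0 g/dL. The other baselines are illustrative assumptions. Grade 3 is taken to run from a 50% fall up to, but not including, a 75% fall.

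**Formulas.** Table hold level = (1 − 0.50) × baseline = 0.50 × baseline. Grade 4 hold level = (1 − 0.75) × baseline = 0.25 × baseline.

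| Baseline | Table holds at or below | Grade 4 wording holds at or below |
|---|---|---|
| Platelets 50,000 (entry minimum) | 0.50 × 50,000 = 25,000 | 0.25 × 50,000 = 12,500 |
| Platelets 150,000 (assumed) | 0.50 × 150,000 = 75,000 | 0.25 × 150,000 = 37,500 |
| Platelets 200,000 (assumed) | below 100,000 (footnote 1) | 0.25 × 200,000 = 50,000 |
| Hemoglobin 8.0 g/dL (entry minimum) | 0.50 × 8.0 = 4.0 | 0.25 × 8.0 = 2.0 |
| Hemoglobin 12.0 g/dL (assumed) | 0.50 × 12.0 = 6.0 | 0.25 × 12.0 = 3.0 |

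In the 200,000 case a 50% fall lands exactly on 100,000, which footnote 1 still counts as Grade 0. The rules therefore disagree from just under 100,000 down to just above 50,000.

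**Does the mismatch reach the statistics?** No. The phase II decision rule counts responses. The grade-based phase II stopping criteria in 16.53 count non-hematologic events only. The hematologic dose-limiting toxicity criteria in 7.16 use CTCAE grades and do not use the 8.3 hold level.

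**The case against.** The strongest reply is that nothing here is contradictory. The sentence does not say Grade 4 only, it sends the reader to the table, and holding at Grade 3 satisfies both texts. Its third ground brings in 8.3 again, and since that table concerns only hemoglobin and platelets, the clause may be meant to catch hematologic events below Grade 4. Section 8.13 acts on any Grade 3 or 4 event, and the 8.3 table follows directly after the sentence. At a hemoglobin of 4.0 g/dL or platelets of 25,000, few clinicians would dose whatever the sentence said.

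Much of this stands. The texts are compatible, and the extreme values are unlikely to be mishandled. The realistic exposure is a mid-range platelet fall, such as from 200,000 to somewhere between 50,000 and 100,000. The mismatch is still not removed:

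- The third ground gives no grade. If it already covered Grade 3 hematologic events, the explicit Grade 4 limit would serve no purpose.
- Section 8.13 sends the reader to the 8.2 table, not to 8.3.
- The catch-all row of Table 8.21 sits in a CTCAE-organised table, while 8.3 grades hemoglobin and platelets on its own scale. It also has different consequences: restart at Grade 0–1 with a 12-week limit and permanent discontinuation at Grade 4. Section 8.3 restarts at Grade 0–2 or baseline, allows 8 weeks at Grade 3, and at Grade 4 holds with discontinuation to be considered. The row supports acting at Grade 3 but cannot stand in for the hematologic rule.

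**Conclusion.** The concern holds. The summary sentence in 8.21 departs by one full grade from the table it cites: a 75% fall in place of a 50% fall. The practical effect is a minor patient-safety ambiguity, limited to drug-related hemoglobin or platelet falls of 50–74% that footnote 1 does not reset. The documents give no frequency for such falls, so the number of patients affected cannot be estimated. The thresholds at the entry minima rest on the protocol's own figures, and those at higher baselines on assumed values. The response-rate endpoint, the 13-of-28 rule, power and type I error are unaffected. The wording should be corrected because a dose-hold rule should give one answer wherever it is read.

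**What to change.** In the bold sentence of 8.21, name Grade 3 or 4 drug-related hematologic toxicity under the 8.3 table as the hold trigger, in place of Grade 4 alone. This adopts the safer threshold already set in the dedicated table and fits 8.13 and Table 8.21, so it calls for no new clinical decision. If the sponsor in fact intended to hold at Grade 4 only, the Grade 3 row of the 8.3 table would have to change, and that would be a clinical decision needing its own justification. The cost is one phrase of protocol wording, with no change to design, sample size or analysis.

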### 8.3 Dose Modification for Hematological Toxicities (Platelet and Hemoglobin only) for all agents

Note: hematological toxicity is not based on CTCAE 4.0 except neutrophil, but based on lymphoma specific hematological toxicity.

#### Dose modification guidelines for drug-related hematological (hemoglobin and platelets) adverse events

Toxicity	Grade 	Decrease from pretreatment	Hold Treatment (Y/N)	Timing for restarting treatment	Dose/Schedule for restarting treatment	Discontinue Subject (after consultation with PI)
NHL specific Hematological Toxicity	1	11-24% decrease in HGB or PLT	No	N/A	N/A	N/A
	2	25-49% decrease in HGB or PLT				
	3	50-74% decrease in HGB or PLT	Yes	Toxicity resolves to Grade 0-2 or baseline	May increase the dosing interval by 1 week	Toxicity does not resolve within 8 weeks of last infusion
	4	$\geq$ 75% decrease in HGB or PLT	Yes	Toxicity resolves to Grade 0-2 or baseline	May increase the dosing interval by 1 week	Permanent discontinuation should be considered for any severe or life-threatening event. Go to observation if $\geq$ 2 cycles of therapy were given, otherwise go to event monitoring

 If, at any level of decrease from the baseline value the platelet and/or hemoglobin counts are within normal limits or platelet count is still  $\geq$  100,000/ $\mu$ L, this will be considered a grade 0.

 If patient has persistent cytopenia, it is recommended to repeat bone marrow evaluation to test if there is disease progression.

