Blood and lymphatic system disorders: immune thrombocytopenic purpura, hemolytic anemia

Immune system disorders: sarcoidosis

Nervous system disorders: Guillain-Barre syndrome, myasthenic syndrome, exacerbation of myasthenia gravis

Gastrointestinal disorders: small intestinal perforation

Skin and subcutaneous tissue disorders: toxic epidermal necrolysis, Stevens-Johnson syndrome, erythema nodosum

The risk profile for pembrolizumab also includes two important potential risks: a) myasthenic syndrome, and b) an increased risk of severe complications (such as early severe graft versus host disease and veno-occlusive disease) of allogeneic transplant in patients with hematologic malignancies who have previously been treated with PD-1 inhibitors.

Patients with multiple myeloma who were treated with pembrolizumab in combination with either pomalidomide or lenalidomide and dexamethasone, had an increased number of serious side effects and deaths as compared to patients who received only dexamethasone and either pomalidomide or lenalidomide. The benefit-risk profile is unfavorable for the combination of pembrolizumab, pomalidomide, and dexamethasone in relapsed refractory multiple myeloma, and the combination of pembrolizumab, lenalidomide, and dexamethasone in newly diagnosed treatment-naive multiple myeloma.

Post marketing reports identified Vogt-Koyanagi-Harada syndrome and hemophagocytic lymphohistiocytosis.

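### Footnote 1 to the Section 8.3 table can be read so that one preserved count sets the combined hematologic grade to 0 despite a Grade 3–4 fall in the other count

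*Combined protocol and SAP*

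**What the plan says.** Section 8.3 sets dose modification for hemoglobin and platelets, for all agents. Its opening note says that "hematological toxicity is not based on CTCAE 4.0 except neutrophil, but based on lymphoma specific hematological toxicity".

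The table has a single toxicity, "NHL specific Hematological Toxicity", with four grades defined by percentage fall from the pretreatment value. Either count can set the grade; Grade 3, for example, is a "50-74% decrease in HGB or PLT". Grades 3 and 4 require treatment to be held. The restart condition for both is "Toxicity resolves to Grade 0-2 or baseline". Discontinuation follows if a Grade 3 toxicity has not resolved within 8 weeks of the last infusion, and is to be considered for severe or life-threatening events at Grade 4.

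Footnote 1 is attached to the table title and to the Grade column. It takes effect if, "at any level of decrease from the baseline value the platelet and/or hemoglobin counts are within normal limits or platelet count is still" at least 100,000/µL. The result is that "this will be considered a grade 0".

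Section 8.21 relies on this grading: pembrolizumab "will be withheld for drug-related Grade 4 hematologic toxicities per table in 8.3".

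**The concern.** The rows say that a fall in either count is enough to produce a grade. The footnote says that a condition met by either count, or by platelets alone, is enough to remove it. The word *this* has no clear antecedent. It could mean the fall in the particular count being graded, or the single combined toxicity that the table defines.

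On the second reading, a deep isolated fall in one count is scored Grade 0 because the other count is preserved. Under the table, Grade 0 calls for no hold, and it also satisfies the restart condition. Two investigators applying the same table to the same blood counts could therefore act differently.

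Isolated falls are foreseeable. Section 15.17 lists, for pembrolizumab, "Blood and lymphatic system disorders: immune thrombocytopenic purpura, hemolytic anemia", and Section 15.202 asks staff to watch blood counts for these disorders.

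**Working it through.** The plan gives no figure to reproduce. The check applies the table and footnote to example counts under three readings.

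**Inputs from Section 8.3.** Grade 1 is an 11–24% fall, Grade 2 is 25–49%, Grade 3 is 50–74%, and Grade 4 is 75% or more. The platelet limb of footnote 1 is 100,000/µL.

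**Assumptions.** The documents give no normal limits, so lower limits of 12 g/dL for hemoglobin and 150,000/µL for platelets are assumed. The counts are illustrative.

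**Formula.** Fall (%) = 100 × (baseline − current) / baseline. The grade before the footnote is the higher of the two counts' grades.

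**Readings of footnote 1.**
- (a) Literal: Grade 0 if either count is normal, or platelets are at least 100,000.
- (b) *And*: Grade 0 if both counts are normal, or platelets are at least 100,000.
- (c) Count by count: each count is exempted only by its own value.

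| Case | Hemoglobin, g/dL (fall) | Platelets, thousands/µL (fall) | Grade before footnote | (a) | (b) | (c) |
|---|---|---|---|---|---|---|
| 1 | 12 to 5.5 (54.2%) | 200 to 180 (10.0%) | 3 | 0 | 0 | 3 |
| 2 | 12 to 3.0 (75.0%) | 200 to 110 (45.0%) | 4 | 0 | 0 | 4 |
| 3 | 13 to 12.5 (3.8%) | 100 to 20 (80.0%) | 4 | 0 | 4 | 4 |
| 4 | 13 to 12.5 (3.8%) | 100 to 40 (60.0%) | 3 | 0 | 3 | 3 |
| 5 | 10 to 5 (50.0%) | 80 to 75 (6.25%) | 3 | 3 | 3 | 3 |
| 6 | 14 to 13.5 (3.6%) | 300 to 110 (63.3%) | 3 | 0 | 0 | 0 |

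Example, case 1: 100 × (12 − 5.5) / 12 = 54.2%. Platelets of 180,000 meet the platelet limb, so (a) and (b) both give 0.

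**What the cases show.**
- Cases 1 and 2: a hemoglobin fall is cancelled under (a) and (b), because the platelet limb carries no hemoglobin condition. This uses only the footnote's own 100,000 and no assumed normal limit.
- Cases 3 and 4: a platelet fall is cancelled only under (a), and only if hemoglobin of 12.5 counts as normal. With a lower limit above 12.5, these cases keep Grades 4 and 3.
- Case 5: when neither condition is met, all readings agree.
- Case 6: the exemption for a platelet count that has fallen but is preserved survives under every reading.

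The table is unchanged for any hemoglobin lower limit above 5.5 and up to 12.5 g/dL, and for any platelet lower limit above 75,000/µL.

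**Restart.** Suppose hemoglobin has fallen from 12 to 5.5 and platelets from 120,000 to 90,000, a fall of 100 × (120 − 90) / 120 = 25%, Grade 2. No exemption applies, the grade is 3 and treatment is held. If platelets recover to 100,000 while hemoglobin stays at 5.5, readings (a) and (b) give Grade 0 and the restart condition is met. Reading (c) still gives Grade 3.

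**The case against.** The best defense is that *this* naturally refers to the decrease being graded. A count that has fallen but remains normal, or platelets still at or above 100,000, is then simply not a toxicity, and *and/or* covers the situation where one or both counts have fallen. The alternative would largely defeat a table that grades a fall in either count. That is probably what the authors meant. It does not settle the matter, because no section says the counts are graded separately, and the table presents one combined toxicity.

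A reader might go further and infer that the footnote and rows contradict each other, or that every isolated Grade 3–4 fall will be scored 0. The documents support neither. A footnote that exempts some cases qualifies the rows; the defect is that its scope is unclear.

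A reader might also infer that the trial's safety analysis is compromised. It is not:
- Section 10.61 has anemia and platelet count graded by CTCAE v4.0 at each evaluation.
- Section 16.241 analyzes thrombocytopenia by nadir and by CTC grade, and tabulates all adverse events.
- The DLT table in Section 7.16 uses CTCAE v4 for platelets. Its closing note counts any event that leads to permanent discontinuation, but that depends on an actual discontinuation, not on the Section 8.3 grade as such.
- The Phase II stopping rule in Section 16.53 counts only non-hematologic events.

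Sections 8.2 and 8.21 also call for withholding pembrolizumab for severe or life-threatening events. This is a partial backstop only, because both refer back to the Section 8 tables.

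Finally, the two cytopenias named in Section 15.17 are listed at below 0.1%. With at most 44 patients, that is fewer than 44 × 0.001 = 0.044 expected cases of each. This limits how often those two diagnoses would matter. It does not bound all large single-count falls, for which the documents give no rate.

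**Conclusion.** The concern holds as an ambiguity in a dose-modification rule. Footnote 1 can be read so that a preserved count sets the combined grade to 0 when the other has fallen by a Grade 3–4 amount. For hemoglobin falls of 50% or more with platelets of at least 100,000/µL, this survives reading *and/or* as *and*. For platelet falls with normal hemoglobin, it requires the literal *or* and depends on the normal limit used.

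The reach is narrow: the hold, restart and discontinuation decisions under Section 8.3, and the Phase I summary in Section 16.241 of significant toxicities as Section 8 defines them. That summary's fallback for Grade 3 or higher events covers only events not described in Section 8, so it does not clearly recover a hemoglobin or platelet fall scored 0. CTCAE-based reporting, DLT assessment, the Phase II stopping rule, the primary endpoint and the error rates are unaffected. How many patients would be graded differently cannot be estimated from the documents. The point merits correction because the rule governs whether treatment is held and the repair is small.

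**What to change.** Reconcile footnote 1 with the grade rows and with the hold and restart rules in Sections 8.21 and 8.3. The text should state:
- which count each Grade 0 exemption applies to; and
- whether a preserved count can override the grade of the other count.

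The same edit should reconcile Section 8.21, which names Grade 4 hematologic toxicity, with the table, which holds at Grades 3 and 4. Section 16.241 then needs no separate change, since it takes its definition from Section 8.

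The grading unit, the thresholds and the resulting actions remain the sponsor's decision. The cost is a reworded footnote and an aligned cross-reference, with no extra tests or visits.
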